3.7.2.7 Response by individual organ

For KD025-213 and KD025-217 organ involvement is captured in the CRF. For KD025-208, the database did not specifically capture baseline organ involvement. Organ involvement was determined as follows:

- All organs, except lungs:
 - If the baseline score is > 0, the organ will be defined as Involved, unless all response assessments are Not Evaluable (NE)
 - If the baseline score is 0, the organ will be defined as Not Involved, unless any response assessment of CR or PR which triggers clinical review to confirm baseline involvement.
- For the lungs:
 - If Forced Expiratory Volume in One Second (FEV1) ≥ 75%, the organ will be defined as Not Involved
 - o If FEV1 < 75%, the organ will be defined as Involved, unless all responses are NE

Kadmon Corporation

Page 18 of 26

The response assessment for the 9 individual organs (skin, eyes, mouth, esophagus, upper GI, lower GI, liver, lungs, and joints and fascia) and global severity rating is categorized into 5 response status: CR, PR, Progression, NE, Stable.

Number and percentage of subjects with best response of CR or PR and total (CR+PR) by individual organ system and global severity rating will be summarized and presented. With the total number of subjects in the Full Analysis Set with involvement of the given organ at baseline as denominator.

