3.11 Exploratory Objectives Analysis

No exploratory analyses will be conducted.

4 APPENDIX A: Kadmon Algorithmic Response Assessments

Baseline Organ Involvement

Organ	Organ Involvement			
Esophagus	NIH Esophagus Score ≥ 1, not entirely explained by non-cGVHD			
	cause			
Upper GI	NIH Upper GI Score ≥ 1, not entirely explained by non-cGVHD cause			
Lower GI	NIH Lower GI Score ≥ 1, not entirely explained by non-cGVHD cause			
Lungs	FEV1 <75% predicted, not entirely explained by non-cGVHD cause			
	If no PFTs available, use NIH lung score ≥ 1, not entirely explained by			
	non-cGVHD cause			
Eyes	NIH Eye Score ≥ 1, not entirely explained by non-cGVHD cause			
Joints and	P-ROM Score <25 (< maximal score) or NIH Joints/Fascia Score ≥ 1,			
Fascia	not entirely explained by non-cGVHD cause			
Skin	NIH Skin Score ≥ 1, not entirely explained by non-cGVHD cause			
Mouth	NIH Modified Oral Mucosal Rating Score ≥ 1, not entirely explained by			
	non-cGVHD cause			
Liver	Elevation > 2x ULN of one or more (ALT, ALP, Total Bilirubin), not			
	entirely explained by non-cGVHD cause			

Response Assessments

Organ	Complete Response	Partial Response	Unchanged	Progression	Non Evaluable
Esophagus	NIH Esophagus Score 0 after previous involvement	Decrease in NIH Esophagus Score by 1 or more points	No change or increase from 0 to 1 in NIH Esophagus Score	Increase in NIH Esophagus Score by 1 or more points, except 0 to 1	NIH esophagus score is Non evaluable
Upper GI	NIH Upper GI Score 0 after previous involvement	Decrease in NIH Upper GI Score by 1 or more points	No change or increase from 0 to 1 in NIH Upper GI Score	Increase in Upper GI Score by 1 or more points, except 0 to 1	NIH upper GI score is Non evaluable
Lower GI	NIH Lower GI Score 0 after previous involvement	Decrease in NIH Lower GI Score by 1 or more points	No change or increase from 0 to 1 in NIH Lower GI Score	Increase in Lower GI Score by 1 or more points, except 0 to 1	If NIH Lower GI score is Non evaluable

Lungs	%FEV1 ≥ 80% after previous involvement; or NIH Lung Symptom Score 0 after previous involvement if PFTs not available	Increase by 10% absolute value of %FEV1; or decrease in NIH Lung Symptom Score by 1 or more points if PTSs not available	Not in the other categories	Decrease by 10% absolute value of %FEV1 and %FEV1 < 75%; or increase in NIH Lung Symptom Score by 1 or more points, except 0 to 1 if PFTs not available	NIH Lung score is Non evaluable and %FEV1 is missing

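### For KD025-208 subjects, the organ-involvement rule in SAP 3.7.2.7 conflicts with SAP Appendix A for liver and for joints/fascia, and can bias the joint response rate upward

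*SAP*

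**What the plan says.** SAP 3.7.2.7 takes baseline organ involvement from two sources. "For KD025-213 and KD025-217 organ involvement is captured in the CRF", whereas "For KD025-208, the database did not specifically capture baseline organ involvement". For KD025-208 it is therefore derived:

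- Every organ other than the lungs follows a single score rule, namely "If the baseline score is > 0, the organ will be defined as Involved, unless all response assessments are Not Evaluable (NE". An organ with score 0 is not involved, "unless any response assessment of CR or PR which triggers clinical review to confirm baseline involvement".
- Lungs: involved if FEV1 is below 75%, again unless every response is NE. Nothing is said about a subject without FEV1.

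The involved subjects in the Full Analysis Set are the denominator for each organ's response rate.

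SAP Appendix A has its own Baseline Organ Involvement table, which is not limited to any parent study. Liver requires "Elevation > 2x ULN of one or more (ALT, ALP, Total Bilirubin". Joints and fascia require "P-ROM Score <25 (< maximal score) or NIH Joints/Fascia Score ≥ 1". Lungs use FEV1 below 75% predicted and add "If no PFTs available, use NIH lung score ≥ 1". For all nine organs, an abnormality wholly due to a non-cGVHD cause does not count. A note under the response table says that an organ uninvolved at baseline may progress but may not score CR or PR. SAP 3.7.1 sends organ response to Appendix A. No sentence says which rule governs KD025-208.

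**The concern.** Involvement settles who is in the organ-response denominator and whether an organ can count as a responder at all. If two sections define it differently, the same subject can be in the denominator under one and out of it under the other, and the programmer must choose. The choice matters most where the rule lets responders back in but not non-responders, because the rate then moves in a known direction.

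The effect is also uneven across dose groups. Protocol 5.2 lists 400 mg QD for KD025-208 only, and SAP 3.2 groups subjects by their original cohort or arm. In any organ table by treatment group, the 400 mg QD column rests entirely on the derived rule, while the 200 mg QD and 200 mg BID columns can mix it with CRF-recorded involvement.

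**Working it through.** The plan gives no organ counts and no figure to reproduce, so the check sets the two rules side by side for every possible value and then illustrates the effect with assumed counts.

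**1. Inputs.** The rules are those in SAP 3.7.2.7 and SAP Appendix A. Score ranges come from the activity form in Protocol Appendix B: joint score 0 to 3; P-ROM sites 1–7, 1–7, 1–7 and 1–4, so the P-ROM total runs from 1+1+1+1 = 4 to 7+7+7+4 = 25. The liver item on that form holds bilirubin, ALT and ALP only.

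**2. Comparison by organ.**

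| Organ | SAP 3.7.2.7 (KD025-208) | SAP Appendix A | Thresholds agree? |
|---|---|---|---|
| Skin, eyes, mouth, esophagus, upper GI, lower GI | score above 0 | score 1 or more | Yes, for every integer score |
| Liver | score above 0 | ALT, ALP or bilirubin above 2 × ULN | No: no liver score is defined |
| Joints and fascia | score above 0 | score 1 or more, or P-ROM below 25 | No |
| Lungs | FEV1 below 75% | FEV1 below 75%; lung score if no PFTs | Same cut; fallback missing |

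Beyond the thresholds, Appendix A has the non-cGVHD-cause exclusion and 3.7.2.7 does not, while 3.7.2.7 has two provisos that depend on post-baseline data (all NE; later CR or PR) and Appendix A has none.

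**3. Joints.** If the score is the NIH joint score, there are 4 × 22 = 88 combinations of joint score (0–3) and P-ROM (4–25). The rules disagree in 21 of them: joint score 0 with P-ROM 4 to 24. If the score is instead read as P-ROM, its minimum of 4 makes every subject involved, including one with a normal 25. Neither reading gives Appendix A.

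**4. Liver.** If the rule is applied to raw laboratory values, being above 0 makes every subject involved. A subject at 1.5 × ULN is then involved under 3.7.2.7 and uninvolved under Appendix A. As written, the rule cannot be programmed for liver without a further decision.

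**5. Direction for joints.** Let R be the responders among D subjects involved under Appendix A, and x the P-ROM-only non-responders. Clinical review can restore P-ROM-only subjects who reach CR or PR; it has no route for the x others. The rate becomes R/(D − x), which exceeds R/D whenever R and x are above 0. Removing all-NE subjects acts the same way.

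**6. Illustration (assumed counts, not from the documents).** R = 8, D = 20, exact Clopper-Pearson 95% intervals:

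| x | Rate | 95% CI |
|---|---|---|
| 0 | 8/20 = 40.0% | 19.1–63.9 |
| 1 | 8/19 = 42.1% | 20.3–66.5 |
| 2 | 8/18 = 44.4% | 21.5–69.2 |
| 4 | 8/16 = 50.0% | 24.7–75.3 |
| 6 | 8/14 = 57.1% | 28.9–82.3 |

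**7. Share of subjects affected.** Protocol 1.4.1 and 1.4.2, at the February 2020 cut-off, allow three ratios: treated in the parent studies, 54/(54 + 132) = 29.0%; still on treatment, 7/(7 + 70) = 9.1%; still participating, 37/(37 + 119) = 23.7%. None is the KD025-208 share of the KD025-217 Full Analysis Set, which the documents do not give.

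**The case against.** The strongest reply is that 3.7.2.7 is a retrospective workaround for a database that lacked the flag, used for one descriptive secondary endpoint in a study with no formal hypothesis. SAP 3.7.1 also repeats ORR and DOR with the investigator's overall assessment, which does not depend on this algorithm. That limits the weight of the point but does not remove it. What was missing was the flag, not necessarily the inputs: Protocol 1.4.1 says that KD025-208 collected blood chemistry and used the 2014 NIH response criteria, and Protocol Appendix C shows that those criteria use liver laboratory values and P-ROM.

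Several stronger readings are tempting and are not supported:

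- **All organs conflict.** For six scored organs the thresholds are identical, and for lungs the FEV1 cut is the same. The missing lung fallback is a gap, not a contradiction.
- **P-ROM is ignored altogether.** A score-0 joint with a later CR or PR goes to clinical review. The loss concerns P-ROM-only subjects without a response.
- **Omitting the non-cGVHD-cause exclusion is an error.** The tick boxes are on the KD025-217 form; nothing shows that KD025-208 recorded them, so this may be a data limit.
- **29% of the analysis is affected.** That is the parent-study share in 2020. It also leaves out the 40 subjects added by KD025-213 Amendment 2, of whom the Companion Study adults can be eligible here.
- **Involvement should be re-derived for everyone.** No defect is shown in the involvement recorded in the CRF for KD025-213 and KD025-217.

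A liver score in the KD025-208 database cannot be excluded, but the SAP defines none.

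**Conclusion.** The point holds for liver and for joints and fascia in KD025-208 subjects, with a smaller gap for lungs without PFTs. For liver the stated rule has nothing to act on. For joints it contradicts Appendix A whenever the NIH score is 0 and P-ROM is below 25, and the KD025-208 joint response rate can be biased upward.

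The size is not known: the number of P-ROM-only joints, the liver counts and the KD025-208 share of the Full Analysis Set are all absent, and the percentages above rest on assumed counts. The upward direction assumes that the score meant for joints is the NIH joint score and that clinical review does restore P-ROM-only responders. Since Appendix A bars CR or PR in an uninvolved organ, that in turn needs response to be assessed before involvement is settled. If review never restored them, responders would be lost too and the direction would be uncertain.

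A reader might infer that dose comparisons or the algorithmic ORR are distorted. The documents do not establish this: no test between doses is specified, and they do not say whether the 3.7.2.7 rule feeds the overall response. The point is worth correcting before analysis, but it does not undermine the study's main descriptive results.

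**What to change.** In SAP 3.7.2.7, for KD025-208 subjects only, derive involvement by applying the Appendix A table to parent-study C1D1 data:

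- liver: ALT, ALP or total bilirubin above 2 × ULN;
- joints and fascia: NIH score of 1 or more, or P-ROM below 25;
- lungs: FEV1 below 75% predicted, or NIH lung score of 1 or more if no PFTs are available;
- other six organs: score of 1 or more;
- all organs: exclude a wholly non-cGVHD cause where KD025-208 recorded it.

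State any condition that the KD025-208 data cannot support. Keep CRF-recorded involvement for KD025-213 and KD025-217. Because the table uses baseline data only, the two post-baseline provisos fall away for KD025-208; if either is to stay, the SAP should say why.

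The cost is a wording change and one extra derivation, with no new data collection. KD025-208 joint response rates may come out slightly lower.

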3.7.2.8 Change in corticosteroid dose

Corticosteroid doses will be presented as mg/kg/day prednisone equivalent dose. Any corticosteroid dose increases to ≥ 0.9 mg/kg PE during the study is counted as new systemic cGVHD therapy.

Descriptive statistics for the Full Analysis Set will be provided for:

- Both prednisone equivalent dose and change-from-baseline values (summary score and domain scores) will be summarized as continuous variables by visit
- Change and % change from baseline to the greatest corticosteroid dose reduction at any post-baseline visit
- Number and % of subjects who reduced systemic corticosteroid dose at any postbaseline visit
- Number and % of subjects who ever discontinued systemic corticosteroid usage at any post-baseline visit

If subjects are not using prednisone as the systemic corticosteroid, then the prednisone dose equivalent will be determined according to following conversion ratios2:

1 mg prednisone is equivalent to:

- 4mg Hydrocortisone
- 0.8mg Methylprednisolone
- 0.15mg Dexamethasone
- 1mg Prednisolone

Kadmon Corporation

Page 19 of 26

0.8mg Triamcinolone

3.7.2.9 Change in cGVHD Global Severity Rating based on the Clinician-reported Global cGVHD Activity Assessment

The Clinician-reported global cGVHD Activity Assessment is a 0-10 point numeric rating scale with a score of 0 indicating "cGVHD symptoms not at all severe" and a score of 10 being "Most severe cGVHD symptoms possible". The activities are assessed on at baseline and then every 3 months after.

Change from baseline in cGVHD severity based on the Clinician-reported global cGVHD Activity Assessment will be summarized as a categorical endpoint at all scheduled assessment visits.

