#### 5.8.1 Corticosteroids

Corticosteroid dose data will be collected throughout the study. Corticosteroids may be tapered at the discretion of the Investigator.

Transient increases in corticosteroid dosing (not exceeding 1 mg/kg/day prednisone equivalent, see Appendix K: Prednisone Dose Equivalents) are permitted for the treatment of cGVHD flare, but the dose must be reduced within 6 weeks. If the dose remains elevated for more than 6 weeks, this will be considered a belumosudil treatment failure.

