3.7.2 Secondary Efficacy Endpoints

3.7.2.1 Duration of Response (DOR)

DOR will be presented according to 5 methodologies:

- The primary definition of DOR is the time from first documentation of response to the time of first documentation of deterioration from best response (e.g., CR to PR, or PR to LR).
- The secondary definition of DOR is the time from first documentation of response to the time of first documentation of lack of response.
- The tertiary definition of DOR is the time from first documentation of response to the time of initiation of new systemic cGVHD therapy.
- The quaternary definition of DOR is the time from first documentation of response to the time of first documentation of lack of response (as the secondary definition) but with durations summed for multiple response/lack of response episodes.
- The FDA definition of DOR is the time from first documentation of response to the time
 of first documentation of organ-level progression, initiation of a new cGVHD therapy, or
 death from any cause, whichever occurs first

The DOR will be reported for early responders, and statistics will include:

- Kaplan-Meier plots and descriptive statistics of DOR. The censoring rules in Table 2 will be applied
- Landmark analyses: Number and percentage of subjects with response sustained for ≥ 3, ≥ 6, ≥ 9, ≥ 12, ≥ 15, ≥ 18, ≥ 24, ≥ 30, ≥ 36 months

Table 2 Censoring Rules for Duration of Response

DOR	Events	Censoring		
Primary	 Deterioration from best response Initiation of new systemic therapy for cGVHD Death 	 Last documented response assessment If LR or initiation of new systemic therapy happens 		

Kadmon Corporation

Page 15 of 26

Secondary	 Documented LR Initiation of new systemic therapy for cGVHD Death 	immediately after two or more missed response assessments, the event date is set as 24 weeks after last documented response assessment prior this event
Tertiary	 Initiation of new systemic therapy for cGVHD Death 	Last response assessment or long term follow up assessment, whichever is the latest and available
Quaternary	 Documented LR Initiation of new systemic therapy for cGVHD Death With summation of DOR from multiple response episodes 	Same as censoring rules for primary and secondary

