FDA defined	 Documentation of organ-level progression Initiation of a new cGVHD therapy Death 	Last documented response assessment If organ-level progression or initiation of new systemic therapy happens immediately after two or more missed response assessments, the event date is set as 24 weeks after last documented response assessment prior this event

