3.7.2.3 Time to Next Treatment (TTNT)

The TTNT will be measured as the time from first treatment to the time of new systemic cGVHD treatment (which will be defined by clinical team review), censored by last response assessment or long term follow up assessment, whichever is the latest and available. TTNT will be analyzed

Kadmon Corporation

Page 17 of 26

by the Kaplan-Meier survival method as well as the landmark analysis at 6, 12, 18, and 24 months.

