3.7.2.4 Failure-free-survival (FFS)

FFS is defined as the absence of new cGVHD systemic therapy, non-relapse mortality and recurrent malignancy (i.e., underlying disease) and is censored by last response assessment or long term follow up assessment, whichever is the latest and available. Kaplan-Meier plots, descriptive statistics of FFS and landmark FFS at 6, 12, 18, 24, 30 and 36 months will be provided. In addition, analyses for the three components of FFS will also be provided.

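### SAP 3.7.2.8 counts any corticosteroid rise to 0.9 mg/kg or more as new cGVHD therapy whatever it was given for, so a course for another illness would, if it enters the dose data, score as a TTNT, FFS or DOR event

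*SAP*

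**What the plan says.** The rule sits in SAP 3.7.2.8, the section on change in corticosteroid dose: "Any corticosteroid dose increases to ≥ 0.9 mg/kg PE during the study is counted as new systemic cGVHD therapy". It sets a threshold in prednisone equivalents (PE) but no indication, minimum duration or exception.

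The term it feeds is an event in three sets of endpoints:

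- **FFS (SAP 3.7.2.4):** "FFS is defined as the absence of new cGVHD systemic therapy, non-relapse mortality and recurrent malignancy".
- **DOR (SAP 3.7.2.1, Table 2):** the primary, secondary, tertiary and quaternary rows list "Initiation of new systemic therapy for cGVHD"; the FDA row lists "Initiation of a new cGVHD therapy".
- **TTNT (SAP 3.7.2.3):** the clock stops at "new systemic cGVHD treatment (which will be defined by clinical team review"). This is the only one of the three that mentions a review.

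The protocol words these failures by what is being treated. Section 6.3 ends TTNT at additional systemic therapy for cGVHD and defines FFS partly by change in cGVHD treatment. Section 5.8 calls the start of new systemic cGVHD therapy a belumosudil treatment failure. Section 5.8.1 says transient steroid increases "are permitted for the treatment of cGVHD flare, but the dose must be reduced within 6 weeks", with the limit "not exceeding 1 mg/kg/day prednisone equivalent".

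**The concern.** The SAP sentence drops the link to cGVHD that the protocol keeps. Transplant recipients can receive systemic steroids for reasons other than cGVHD. Read as written, a brief course for such a reason that reaches the threshold is new cGVHD therapy, and the subject fails on FFS and TTNT and, if a responder, on DOR.

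These endpoints would then partly measure intercurrent illness instead of loss of cGVHD control. The study has no formal hypothesis (Protocol 9.1), so its descriptive time-to-event estimates are the efficacy result, and what counts as an event determines what they mean.

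**Working it through.** The plan gives no event rate or power figure to reproduce, so the main check is textual.

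**1. Does anything restrict the rule by indication?** SAP 3.7.2.8 does not. The review in 3.7.2.3 could, but it is stated only for TTNT, has no criteria, and is not said to take precedence over the 0.9 mg/kg rule. Elsewhere the SAP names a review trigger when it wants one: 3.7.2.7 sends certain organ-involvement cases to clinical review. Section 3.7.2.8 names none.

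**2. Do steroids given for other illnesses enter the dose data?** The documents leave this open.

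| Place | Reading it supports |
|---|---|
| Protocol 3.1 and SAP 2.2: steroid dosage listed together with other cGVHD therapies | cGVHD steroids only |
| Protocol Table 7: steroid dosage under efficacy, concomitant medications under safety | cGVHD steroids only |
| Protocol 5.8.1: steroid dose collected throughout, no restriction stated | all steroids |
| Protocol 5.8: all concomitant medications recorded | all steroids are at least available |

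**3. When can the rule operate within KD025-217?** Table 7 ends collection of steroid dosage 28 days after last dose. After that, LTFU contacts (Protocol 6.2.5) ask about survival, new systemic cGVHD therapies and relapse, not steroid dose. Subjects who enter already in LTFU have only those contacts (Protocol 6.2.2). The same non-cGVHD course could therefore be an event on treatment and not an event in LTFU. The event definition changes at end of treatment, and differs between subjects enrolled on treatment and subjects enrolled in LTFU.

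**4. How high is the threshold?** Threshold dose = 0.9 × weight × SAP conversion ratio. At an assumed 70 kg, 0.9 × 70 = 63 mg prednisone. That equals 63 × 0.15 = 9.45 mg dexamethasone, 63 × 4 = 252 mg hydrocortisone, or 63 × 0.8 = 50.4 mg methylprednisolone. With no minimum duration, one day at that level suffices.

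**5. What does one false event weigh?** With the planned 70 subjects and no censoring before the landmark:

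- 1 event: 1/70 = 1.4 points
- 3 events: 3/70 = 4.3 points
- 5 events: 5/70 = 7.1 points

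**6. Range under assumed rates.** Suppose non-cGVHD courses reaching the threshold occur at a constant rate r per patient-year, independently of true failure, in subjects treated with dose captured throughout. Then observed S(t) = true S(t) × exp(−r·t), and the share falsely failed in the absence of other events is 1 − exp(−r·t). At t = 2 years, with an assumed true FFS of 60%:

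| r (assumed) | Falsely failed by 24 months | Observed FFS |
|---|---|---|
| 0.01 | 2.0% | 58.8% |
| 0.03 | 5.8% | 56.5% |
| 0.05 | 9.5% | 54.3% |
| 0.10 | 18.1% | 49.1% |

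Neither the rates nor the 60% come from the documents. Across the whole enrolled set the effect at a given r would be smaller, because subjects in LTFU are not exposed to the rule.

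**The case against.** A reader might infer that steroids for other illnesses will certainly become false failures on all three endpoints. The documents do not support that. The clinical team review covers the very term at issue, is explicit for TTNT, and might in practice be used for FFS and DOR. The efficacy dose record may hold only cGVHD steroids, with other courses kept as concomitant medication. No programming is shown. No rate is given, so the effect could be close to zero. These points stand, and they make the problem conditional.

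A fixed dose threshold also has merit in an open-label study: it is objective, and its error runs against the drug. Restricting the rule to an attributed indication brings in judgement that could err the other way. This too stands, and it is a reason to keep the all-cause count as a sensitivity analysis. With no hypothesis test, no formal decision depends on the rule.

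None of this supplies the missing condition. A review without criteria, mentioned for one endpoint, does not tell the analyst what to do with a non-cGVHD course in FFS or DOR when the only explicit instruction is to count it.

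**Conclusion.** The SAP rule is broader than the event concept in the protocol and in its own endpoint definitions. As written it can record a failure in a subject whose cGVHD is controlled. The gap is clearest for FFS and DOR, where no review is stated; for TTNT the review may close it. The change of definition at end of treatment is a second, related inconsistency.

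The direction is towards more and earlier failures. The size is unknown: about 1.4 points per false event if all 70 subjects are the denominator, with fewer than 70 able to incur one. The conclusion assumes that at least some non-cGVHD steroid dosing reaches the data behind the rule, which the documents neither establish nor exclude. It does not support a claim that the results will be materially wrong, or that the rule favours belumosudil.

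A separate conflict in the same SAP sentence concerns steroids that are given for cGVHD. A transient flare increase to between 0.9 and 1 mg/kg/day, reduced within 6 weeks, is allowed by Protocol 5.8.1 but is an event under the SAP. An increase that stays below 0.9 mg/kg for more than 6 weeks is a protocol failure that the SAP sentence does not catch. Those passages must be reconciled; this point takes no position on which is right, and reconciling dose and duration alone would leave the indication open.

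**What to change.** In the SAP:

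1. In 3.7.2.8, limit the rule to increases in systemic corticosteroid given for cGVHD.
2. State that the clinical team review already planned in 3.7.2.3 applies to TTNT, FFS and DOR alike, with written criteria, and is completed before database lock. It settles the indication where that is unclear.
3. List courses that reach the threshold for other reasons.
4. Keep the all-cause count at 0.9 mg/kg or more as a sensitivity analysis for the three endpoints.

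The cost is a few sentences of SAP text and one repeat of the event derivation, with no new visits. There are two downsides. Classifying the indication in an open-label study involves some discretion, which the sensitivity analysis makes visible. The documents also do not show that an indication field is captured, so the review would have to rely on concomitant medication records and on the AE record, where Protocol 7.3.4 asks how each event was treated.

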#### 5.8 Concomitant Medications and Procedures

All concomitant medications including dietary/herbal/over the counter supplements taken during the study and relevant procedures will be recorded. Initiation of new systemic cGVHD therapy will be considered a new line of treatment and a belumosudil treatment failure.

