### 6.3 Efficacy Endpoints

The efficacy endpoints of this study will be:

- Duration of Response (DOR)
- Change in LSS (Appendix D: Lee cGVHD Symptom Score)

- Time to Next Treatment (TTNT): defined as the time from the first dose of belumosudil to the start of additional systemic cGVHD therapy
- FFS: defined as the absence of cGVHD treatment change, non-relapse mortality, and recurrent malignancy
- Overall Survival (OS): defined as the time from first dose of belumosudil to the date of death due to any cause
- Percentage of subjects who have a best response of CR and percentage of subjects who have a best response of PR
- Response by individual organ
- Change in corticosteroid dose: the change in prednisone equivalent dose of corticosteroids (mg/kg/day) during the study
- Change in cGVHD Global Severity Rating using the Clinician-reported Global cGVHD Activity Assessment (Appendix B: Clinician-reported Global cGVHD Activity Assessment)

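### The SAP counts any steroid increase to 0.9 mg/kg or more as new cGVHD therapy, without an indication or duration condition, and so departs from protocol 5.8.1 in both directions

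*SAP*

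**What the plan says.** The operative sentence is in SAP 3.7.2.8, the section on steroid dose summaries: "Any corticosteroid dose increases to ≥ 0.9 mg/kg PE during the study is counted as new systemic cGVHD therapy". No duration, indication or confirmation step is attached.

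That status feeds three endpoints. New systemic cGVHD therapy is the TTNT event (SAP 3.7.2.3), one of the three FFS components (SAP 3.7.2.4), and a listed event in all five DOR definitions (SAP 3.7.2.1, Table 2). For TTNT only, SAP 3.7.2.3 adds that the clinical team will decide by review what counts as new treatment.

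The protocol treats steroids differently. Under 5.8.1, transient increases ("not exceeding 1 mg/kg/day prednisone equivalent") "are permitted for the treatment of cGVHD flare, but the dose must be reduced within 6 weeks". It continues: "If the dose remains elevated for more than 6 weeks, this will be considered a belumosudil treatment failure". Section 5.8 adds: "Initiation of new systemic cGVHD therapy will be considered a new line of treatment and a belumosudil treatment failure". In section 6.3, TTNT is "defined as the time from the first dose of belumosudil to the start of additional systemic cGVHD therapy" and FFS is "defined as the absence of cGVHD treatment change, non-relapse mortality, and recurrent malignancy".

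**The concern.** A reader who takes 5.8.1 as the rule for when a steroid increase counts against belumosudil will expect a failure to depend on duration. The SAP makes it depend on dose alone. The same course can then be acceptable under one document and an endpoint event under the other, or the reverse.

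The SAP sentence also does not require that the steroid be given for cGVHD. A course given for another illness is neither additional cGVHD therapy nor a change in cGVHD treatment, so counting it would fit none of the three endpoints.

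TTNT, FFS and DOR are among the study's main efficacy outputs. The study tests no hypothesis (protocol 9.1), so error rates are not in question. What is at stake is whether the estimates mean what protocol 6.3 says, and whether two programmers would derive the same values from the same data.

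**Working it through.** The plan gives no event count or expected rate here, so there is no figure to reproduce. The check sets the rules side by side and then sizes one reclassified subject.

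**Step 1. Courses under each rule** (protocol 5.8.1; SAP 3.7.2.8 read literally; doses in mg/kg/day prednisone equivalent)

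| Course | Protocol 5.8.1 | SAP 3.7.2.8 |
|---|---|---|
| cGVHD flare, below 0.9, 6 weeks or less | permitted | not counted |
| cGVHD flare, below 0.9, more than 6 weeks | failure | **not counted** |
| cGVHD flare, 0.9-1.0, 6 weeks or less | permitted | **counted** |
| cGVHD flare, 0.9-1.0, more than 6 weeks | failure | counted |
| cGVHD flare, above 1.0, 6 weeks or less | not permitted, but not named a failure | counted |
| Non-cGVHD reason, 0.9 or more | not addressed | counted, if in the steroid data |

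Rows 2 and 3 disagree in opposite directions.

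**Step 2. Which endpoints row 3 reaches**
- TTNT: an event under the literal rule, unless the clinical team review excludes it.
- Tertiary DOR: an event, since only new therapy or death ends it.
- Other four DOR definitions: arguable, because the flare may already register as deterioration, lack of response or organ progression.
- FFS: arguable, because a flare increase could be a treatment change in the sense of protocol 6.3.

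**Step 3. Which endpoints row 2 reaches**
The protocol calls this a treatment failure but does not say that such a failure is itself a TTNT or FFS event. It could be a treatment change under the protocol's FFS wording. The SAP dose rule does not pick it up.

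**Step 4. Where the threshold lies** (body weights are assumptions)
- Permitted flare band, 0.9 to 1.0 x weight: 45-50 mg/day prednisone at 50 kg, 63-70 at 70 kg, 81-90 at 90 kg.
- By the SAP's conversion ratios, 0.9 mg/kg prednisone equals 0.9 x 0.15 = 0.135 mg/kg dexamethasone, 0.9 x 0.8 = 0.72 mg/kg methylprednisolone, or 0.9 x 4 = 3.6 mg/kg hydrocortisone. At 70 kg that is 9.45, 50.4 and 252 mg.

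**Step 5. Size per subject**
- Approximately 70 subjects (protocol 4.1): 1/70 = 1.4 points on a crude proportion. Illustratively, 3/70 = 4.3 and 7/70 = 10.0 points; these counts are assumptions.
- DOR, if responders match the parent-study rates of 64.8% to 73.5% (assumption): 70 x 0.648 = 45.4 and 70 x 0.735 = 51.5 responders, so 1/45.4 = 2.2 and 1/51.5 = 1.9 points. If all 70 are responders, 1.4 points.

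The shift goes down for rows 3 and 6. It would go up for row 2, relative to an analysis that counted those failures.

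**The case against.** The strongest reply is that TTNT, FFS and DOR rest on the same event and that SAP 3.7.2.3 sends that event to clinical review, so one adjudicated list could serve all three. That is a natural reading, and for TTNT the safeguard is explicit. But the SAP gives no review criteria, does not extend the review to FFS or DOR, and does not say whether it overrides the unconditional dose sentence.

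Second, the steroid record may hold cGVHD treatment only. Protocol 3.1 pairs steroid dosage with other cGVHD therapies, and Appendix A lists it under efficacy assessments, apart from concomitant medications. This may well be right, and it makes the non-cGVHD case conditional. It is not settled: 5.8.1 collects dose data without naming an indication, all concomitant medications "taken during the study and relevant procedures will be recorded", and the SAP does not name its source. The dexamethasone and other equivalents show where the threshold lies, not that such courses would be counted.

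Third, a fixed threshold is a legitimate definition, only flare courses in the top tenth of the permitted dose range conflict, and 5.8.1 does not say that a shorter course can never be an endpoint event. All of that stands, and it is why the threshold itself need not be replaced.

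A reader might also infer that the SAP rule can only add events and so is simply conservative for belumosudil. The documents do not support this: increases below 0.9 mg/kg lasting more than 6 weeks are protocol failures that the rule leaves out.

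**Conclusion.** The point holds as a two-way mismatch between a stated SAP rule and protocol 5.8.1. Read literally, the SAP counts permitted 0.9-1.0 mg/kg/day flare courses of 6 weeks or less, and non-cGVHD courses if they are in the steroid data. It does not count lower-dose increases that outlast 6 weeks.

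The documents do not show how many subjects fall in either group, so neither the net direction nor the total effect can be determined. The figure of 1.4 points per subject assumes a crude proportion with all 70 in the denominator. Subjects who enter in long-term follow-up have no steroid dose collected in this study, and a subject weighs more within a single dose group.

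It would go too far to conclude that every such course becomes a TTNT, FFS and DOR event. Clinical review may remove it from TTNT, the FFS case is arguable, and four of the five DOR definitions may already count the flare. This is a worthwhile, inexpensive clarification of a descriptive analysis.

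**What to change.** Amend SAP 3.7.2.8 as follows.

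- Keep 0.9 mg/kg as the primary threshold, but limit it to increases given for cGVHD. Take the indication from the concomitant medication record or, where it is not recorded there, from clinical review.
- Apply the clinical team review of SAP 3.7.2.3 identically to TTNT, FFS and DOR, and say whether it can override the dose rule.
- Add a sensitivity analysis of the three endpoints under the 5.8.1 rule: an increase for cGVHD, at any dose, still elevated after more than 6 weeks. Specify in advance the reference for an elevated dose, the event date, and the handling of courses above 1 mg/kg/day.
- State whether the rule covers the parent-study period, since TTNT starts at the first belumosudil dose.

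The cost is SAP wording, some clinical review of steroid indication (the documents do not show it as a CRF field) and one extra analysis run. No protocol amendment is needed. One limit remains: Appendix A collects steroid dose only until 28 days after the last dose of study drug, so neither rule can be applied from dose data in long-term follow-up. The SAP should say so.
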